5.0 Grouping Factors

NONE

6.0 Registration Procedures

6.11

6.1 Initial Registration

Friday).

To register a patient, access the ACCRU web page at
go to the Remote Application
section, click on "Registration" and enter the registration/randomization
application. The registration application is available 24 hours a day, 7 days a
week. Back up and/or system support contact information is available on the
Web site. If unable to access the Web site, call the Academic and Community
Cancer Research United (ACCRU) Registration Office at
between the hours of 8 a.m. and 4:30 p.m. Central Time (Monday through

Instructions for the registration application are available on the above web page under the Remote Application section, "Remote Application Training."

Prior to initiation of protocol study intervention, this process must be completed in its entirety and an ACCRU subject ID number must be available as noted in the instructions. It is the responsibility of the individual and institution registering the patient to confirm the process has been successfully completed prior to release of the study agent. Patient registration via the registration/randomization application can be confirmed in any of the following ways:

- Contact the ACCRU Registration Office III If the patient was fully registered, the Registration Office staff can access the information from the centralized database and confirm the registration.
- Refer to "Remote Registration, Installation & Entry Instructions" under "Training Material Manuals."

6.2 Subsequent Registrations

6.21 To register a patient, fax () a completed eligibility checklist to the Academic and Community Cancer Research United (ACCRU) Registration Office between 8 a.m. and 4:30 p.m. central time Monday through Friday.

NOTE: Patients have the option to register on COLOMATE for a maximum of 3 times or at the discretion of the Study Chair. Patients must reconsent and meet eligibility criteria in section 3 and will receive a new patient ID.

- 6.3 At the time of registration, the following will be recorded:
 - Patient has given permission to share his/her data for future research to learn about, prevent, or treat cancer or other health problems (for example: diabetes, Alzheimer's disease, or heart disease).
 - Patient has given permission for ACCRU to share his/her data to outside researchers.
- 6.4 Documentation of IRB approval must be on file with ACCRU before an

investigator may register any patients. Approvals should be uploaded through the online ACCRU Regulatory Management System (ARMS).

In addition to submitting initial IRB approval documents, ongoing IRB approval documentation must be on file with ACCRU no less than annually. Approvals should be uploaded through the online ACCRU Regulatory Management System (ARMS). If the necessary documentation is not submitted in advance of attempting patient registration, the registration will not be accepted and the patient may not be enrolled in the protocol until the situation is resolved.

Submission of annual IRB approvals to ACCRU is required until the study is closed through your IRB*.

*Please note, if the study site IRB determines that the study meets requirements for a minimal risk study, per the Revised Common Rule, any study approved after January 21, 2019, is not required to provide continuing/annual reviews.

- 6.5 Prior to accepting the registration, the registration application will verify the following:
 - IRB approval at the registering institution
 - Patient eligibility
 - Existence of a signed consent form
 - Existence of a signed authorization for use and disclosure of protected health information
- 6.6 Study-specific activities cannot begin prior to registration and must begin ≤30 days after registration.
 - NOTE: Guardant360 testing completed ≤ 60 days prior to registration will be accepted.
- 6.7 Pretreatment tests/procedures (see Section 4) must be completed within the guidelines specified on the test schedule.
- 6.8 Study-specific activities on this protocol must commence at an ACCRU institution under the supervision of a medical oncologist.
- 6.9 Blood draw kits are available on site.

EXEMPTION: Guardant360 tests completed \leq 60 days prior to registration will be accepted.

7.0 Protocol Treatment

This is a screening protocol to identify genomic alterations via cfDNA and facilitate enrollment onto COLOMATE companion clinical trials. Standard genomic profiling will be performed using the Guardant360 assay in Guardant Health's CLIA-certified laboratory. Guardant360 is a commercially available cfDNA genotyping assay; the genomic results from Guardant360 may be used in conjunction with other data to guide patient care. Guardant360 is not being used as an investigational device in this study, nor is the purpose to validate its use in patient selection for study treatments.

7.1 Guardant 360 test

7.11 Patients who had Guardant360 test completed ≤60 days prior to registration.

If the patient has received Guardant 360 testing ≤60 days prior to registration, these test results will be accepted for study and cell-free DNA analysis will not be repeated.

To receive test results, if not already available, the patient will fill out the Authorization to Use and Disclose Health Information form found on the ACCRU website under Manuals and Forms that the treating physician/CRA will fax to Guardant Health.

7.12 Patients who do not have Guardant360 results or Guardant360 results completed >60 days prior to registration.

Follow section 14 to submit blood samples to Guardant Health.

- 7.2 Site access to Guardant360 testing results
 - 7.21 Patients who had Guardant360 results completed ≤60 days prior to registration.

Guardant will send the results to the site contacts they list on the authorization form. Sites will then email the de-identified results (including ACCRU patient ID) to

7.22 Patients who do not have Guardant360 results or Guardant360 results completed >60 days prior to registration.

Sites will access Guardant360 results through the Guardant Health portal:

Following receipt of results, sites must email the de-identified results (including ACCRU patient ID) to

See detailed instructions on the ACCRU website under Manuals and Forms.

- 7.3 COLOMATE Committee Recommendation
 - 7.31 At the time of Guardant360 kit submission or at the time of faxing authorization form to Guardant Health, sites will complete the top portion of the COLOMATE Companion Trial Recommendation Form and email to

The COLOMATE steering committee will complete the form and send the treating physician/CRA the COLOMATE Companion Trial Recommendation form with companion trial recommendations within 5 business days of receipt of Guardant360 test results. If a patient qualifies to be screened for a companion clinical trial, the treating physician/CRA will provide this form to the appropriate companion trial study team.

COLOMATE recommendations are not binding and the local investigator and/or

treating physician may determine the preferred companion trial taking into consideration best clinical evidence and the patient's clinical circumstances.

If additional assistance with companion trial recommendations are needed, local investigators and/or treating physicians may contact the COLOMATE steering committee at

- 7.32 Actionable alteration is defined as a genomic alteration/mutation profile that qualifies a patient to be screened for one companion trial.
- 7.4 Patients for whom 1 actionable alteration is identified

If an actionable alteration is identified, the treating physician will be notified of any available COLOMATE companion trials on the COLOMATE Companion Trial Recommendation Form.

- 7.41 Patients who choose to enroll in a COLOMATE companion trial and meet eligibility criteria will be treated according to that companion trial protocol.
- 7.42 Patients who decline participation on the COLOMATE companion trial or do not meet eligibility criteria can subsequently register with COLOMATE ≥60 days after previous registration for a maximum of 3 times or at the discretion of the Study Chair.
- 7.5 Patients for whom ≥ 2 actionable alterations are identified

If more than one actionable alteration is identified, COLOMATE companion trial recommendations will be prioritized according to the following algorithm: 1) fusions; 2) amplifications; 3) all other alterations. If the algorithm does not assign a patient to one companion clinical trial, the report will be referred to the COLOMATE PI and/or a COLOMATE steering committee designee and statistician for adjudication.

- 7.51 Patients who choose to enroll in a COLOMATE companion trial and meet eligibility criteria will be treated according to that companion trial protocol.
- 7.52 Patients who decline participation on a COLOMATE companion trial or do not meet eligibility criteria can re-register with COLOMATE ≥60 days after previous registration for maximum of 3 times or at the discretion of the Study Chair.
- 7.6 Patients for whom no actionable alteration is identified

If no actionable alteration is identified, the treating physician will be notified of any other COLOMATE companion trials for which the patient may be eligible on the COLOMATE Companion Trial Recommendation Form. The patient can re-register with COLOMATE ≥60 days after previous registration for maximum of 3 times or at the discretion of the Study Chair.

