3.0 Patient Eligibility

- 3.1 Inclusion Criteria
 - 3.11 Age \geq 18 years.

- 3.12 Histological confirmation of adenocarcinoma of the colon or rectum that is metastatic and/ or unresectable.
- 3.13 Progression, intolerance, or contraindication to a fluoropyrimidine (e.g., 5-fluorouracil or capecitabine), oxaliplatin, irinotecan, an anti-VEGF monoclonal antibody (bevacizumab, ziv-aflibercept, or ramucirumab), and an anti-PD-1 monoclonal antibody (nivolumab or pembrolizumab) if tumor has deficient mismatch repair proteins (dMMR) or is microsatellite instability-high (MSI-H).
- 3.14 For patients with *KRAS* and *NRAS* wild-type tumors, progression, intolerance, or contraindication to an anti-EGFR monoclonal antibody (cetuximab or panitumumab). Note: If tissue is known to be positive for HER2 expression (IHC 3+) or the tumor has *ERBB2* (HER2) amplification detected by a CLIA-certified assay, prior treatment with anti-EGFR therapy is not required.
- 3.15 At least one site of disease that is measurable by RECIST criteria (version 1.1) that has not been previously irradiated; if the patient has had previous radiation to the target lesion(s), there must be evidence of progression since the radiation (see section 11).
- 3.16 Life expectancy \geq 3 months per estimation of investigator.
- 3.17 ECOG Performance Status (PS) 0, 1, or 2 (Form is available on the ACCRU web site
- 3.18 Capable of understanding and complying with the protocol requirements and has signed the informed consent document.
- 3.19 Satisfy at least one of the following two conditions:
 - Willing and able to provide blood sample for screening purposes (See Section 14.0).
 - Guardant360 testing completed ≤ 60 days prior to registration is available for COLOMATE steering committee to review.

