16.5 Analysis Plan

16.51 Primary Endpoints

For the analysis of the first primary endpoint, the proportion of patients who
have an actionable genomic profile will be calculated. This is defined as the
total number of eligible patients who have an actionable genomic profile
divided by the total number of eligible patients whose genomic profile is
available for COLOMATE steering committee review.

A patient may come back to ACCRU-GI-1611 for subsequent screening (see sections 7.5, 7.5, and 7.6); therefore, a patient can contribute information to the first primary endpoint more than once.

- Our goal is to have at least 20% of patients have actionable genomic profile. The endpoint will be presented as a point estimate along with a 95% confidence interval (by Wald asymptotic confidence limit).
- For the analysis of the second primary endpoint, the proportion of patients that enroll in the companion trial recommended by the COLOMATE committee will be calculated. This is defined as the total number of eligible patients that enroll in the recommended companion trial divided by the total number of eligible patients who have an actionable genomic profile.

A patient may come back to ACCRU-GI-1611 for subsequent screening (see sections 7.4, 7.5, and 7.6); therefore a patient can contribute information to

the second primary endpoint more than once.

• Our goal is to enroll at least 75% of patients who have an actionable genomic profile. The endpoint will be presented as a point estimate along with a 95% confidence interval (by Wald asymptotic confidence limit).

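### A patient who re-registers soon after day 60 can have the same Guardant360 result counted twice in the primary endpoints, because the 60-day re-registration rule and the 60-day prior-test rule overlap

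*Combined protocol and SAP*

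**What the plan says.** **Re-registration.** A patient with one actionable alteration who declines the companion trial or is not eligible for it "can subsequently register with COLOMATE ≥60 days after previous registration" (7.42). The same 60-day minimum applies after two or more actionable alterations (7.52) and after none (7.6: "The patient can re-register with COLOMATE ≥60 days after previous registration"). Section 6.2 asks for new consent, Section 3 eligibility and a new patient ID. It does not ask for a new sample.

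**Prior tests.** Criterion 3.19 can be met if "Guardant360 testing completed ≤ 60 days prior to registration is available for COLOMATE steering committee to review". For such a test, 7.11 states that "these test results will be accepted for study and cell-free DNA analysis will not be repeated". Section 4.0 (footnote 2) and 14.1 say the same, and 6.6 and 6.9 also accept these tests. A new draw is directed only under 7.12, headed "Patients who do not have Guardant360 results or Guardant360 results completed >60 days prior to registration".

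**Timing of the study test.** Under 6.6, study activities cannot precede registration and "must begin ≤30 days after registration".

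**Analysis.** Section 16.51 says that "a patient can contribute information to the first primary endpoint more than once", and repeats this for the second primary endpoint. Both proportions are to be reported with a 95% Wald interval. No rule covers a reused test result or repeated records from one patient.

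**The concern.** The two 60-day limits meet at the same point. A test performed on study after the first registration is usually no more than 60 days old when re-registration opens. In that overlap the text does more than permit reuse: it says the assay is not repeated. The patient comes back under a new ID, brings no new genomic information, and adds a second record to the first primary endpoint. If that record is actionable, it also enters the denominator of the second.

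The two proportions and their intervals are the whole primary output of this descriptive study, and each carries a numerical goal (20% and 75%). A result counted twice makes the interval look more precise than it is. If those who return differ from those who do not, it also shifts the estimate.

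**Working it through.** **1. The plan's own figure.** Section 16.4 gives (35.71%, 44.29%) for 40% of 500. The Wald formula p ± 1.96·√(p(1−p)/n) gives 0.40 ± 1.96·√(0.24/500) = 0.40 ± 0.0429, which agrees. It treats the 500 records as independent. (The 20% row prints a lower limit of 14.49%, where the formula gives 16.49%. That is a separate misprint and is not used here.)

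**2. The reuse window.** Let the first registration be day 0, test completion day t, and re-registration day r. Re-registration is open if r ≥ 60. The old test is accepted if its age r − t ≤ 60, that is, r ≤ 60 + t. The values of t are assumed.

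| t | Days on which the old test is reused |
|---|---|
| 0 | 60 only |
| 7 | 60–67 |
| 14 | 60–74 |
| 30 | 60–90 |

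Two limits follow:
- A test completed before the first registration (t ≤ −1) is at least 61 days old on day 60 and cannot be reused.
- A third registration is no earlier than day 120. A third use would need 120 − t ≤ 60, so t ≥ 60, which does not fit the planned timing. One test therefore counts at most twice.

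**3. Precision.** Hold the record count at 500 and let d of them be second counts that repeat the first outcome. Then 500 − 2d results count once and d count twice. If returning is unrelated to outcome, the variance relative to the nominal value is [(500 − 2d) + 4d]/500. Effective n is 500 divided by this ratio, and coverage is 2Φ(1.96/√ratio) − 1. The values of d are assumed.

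| d (share) | Variance ratio | Effective n | Correct half-width at 20% (nominal 3.51 points) | Actual coverage of the nominal 95% interval |
|---|---|---|---|---|
| 25 (5%) | 550/500 = 1.10 | 455 | 3.68 | 93.8% |
| 50 (10%) | 600/500 = 1.20 | 417 | 3.84 | 92.6% |
| 100 (20%) | 700/500 = 1.40 | 357 | 4.15 | 90.2% |

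**4. First endpoint, point estimate.** Start from 100 actionable among 500 distinct results, 20.0%, and add 50 copies (assumed):
- all non-actionable (7.6 returners): 100/550 = 18.2%;
- all actionable (7.42 and 7.52 returners): 150/550 = 27.3%.

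**5. Second endpoint, point estimate.** Start from 150 enrolled among 200 actionable, 75.0%, and let 20 non-enrollers return on the same test (assumed):
- none enrols: 150/220 = 68.2%;
- all enrol: 170/220 = 77.3% by record, against 170/200 = 85.0% by patient.

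**The case against.** **The look-back was meant for outside tests.** Sections 7.11 and 7.21 obtain a prior result through an authorization form, while on-study results come through the portal (7.22). Section 14.4 mentions testing outside COLOMATE separately. This makes the intent plausible, but no section restricts the exemption to such tests, and the form is needed only when the result is not already to hand.

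**The window is short.** This stands. Section 4.0 places the assay at registration/baseline. If completion is read as a draw on day 0, only day 60 is affected. Section 18.1 lists Guardant360 results among the baseline material due 30 days (±3) after registration, so a much later t is not what the plan foresees.

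**A second review need not repeat the first.** This also stands. The first endpoint is defined by the recommendation, not by the assay, and 16.4 says that companion trials are still being opened. The genomic input is the same, but the outcome can change. The coverage figures apply only to second counts that repeat the first outcome.

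**Correlation arises with fresh samples too.** True. Section 16.51 allows repeat contributions in general, and within-patient correlation is a wider matter. Reuse of one result with an unchanged outcome is its extreme case.

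**Stronger readings.** A reader might infer that the copies pull both proportions down. The documents do not support this for the first endpoint, because 7.42 and 7.52 returners have actionable alterations and their copies raise it. A reader might also infer that the overlap defeats the purpose of re-screening. No section gives finding new alterations as the reason for re-registration, and 7.12 directs a fresh draw once the earlier test is more than 60 days old.

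**Conclusion.** The concern holds with a limited scope. Followed as written, the rules allow one on-study Guardant360 result to be entered twice, under two patient IDs, in an analysis that treats the entries as independent. This happens only when the test was completed on or after the first registration and the patient returns between day 60 and day 60+t. It happens at most once per test under the planned timing.

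The interval is too narrow whenever second counts repeat the first outcome: coverage is about 94% to 90% for an assumed 5% to 20% of records. The sign of the bias in the first endpoint is unknown in advance. The second endpoint falls if returning non-enrollers again do not enrol. The documents give neither a re-registration rate nor a turnaround time, so every size quoted rests on assumed counts and on assumed t, and the real effect may be small. The correction is still worth making, because the text directs the reuse and the remedy costs very little.

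**What to change.** - **Section 16.51:** state that each Guardant360 result counts once in each primary endpoint. If the same result is reviewed again against newly opened companion trials, record this as an updated recommendation on the existing record rather than as a new one.
- **Sections 6.2, 7.11, 7.12 and 14.1:** reconcile them so that, at a subsequent registration, the prior-test exemption applies only when the sample was collected after the one used at the previous registration.

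The cost is a few sentences. A few early re-registrants would use the baseline test that 19.2 already lists as research funded, and the number of records in the analysis would fall slightly. Counting each result once does not settle how repeat records based on fresh samples are handled. The plan should address that separately, for example with a first-registration-only analysis or patient-clustered intervals.

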7.7 Evaluation procedures

7.71 Each patient will be contacted by telephone 30 days (\pm 3 days) after registration to document the patient's status of registration to a companion study. This

information is needed to complete the On-Study form.

8.0 Dosage Modification Based on Adverse Events

None for this screening protocol.

9.0 Ancillary Treatment/Supportive Care

None for this screening protocol.

10.0 Adverse Event (AE) Reporting and Monitoring

Adverse Events will not be collected for this screening protocol.

11.0 Treatment Evaluation Using RECIST Guideline

NONE

12.0 Descriptive Factors

- 12.1 Microsatellite instability (MSI)/Mismatch repair (MMR) status (MSI-H/deficient MMR vs. MSS/ proficient MMR)
- 12.2 KRAS (mutated vs. wildtype)
- 12.3 NRAS (mutated vs. wildtype)
- 12.4 BRAF V600E (mutated vs. wildtype vs. unknown)
- 12.5 Primary tumor site: Cecum, ascending colon, hepatic flexure, transverse colon, splenic flexure, descending colon, sigmoid colon, rectosigmoid junction, rectum vs. unknown vs. multiple

13.0 Treatment/Follow-up Decision at Evaluation of Patient

This is a screening protocol and patients will not receive any treatment.

- 13.1 A patient is deemed *ineligible* if after registration, it is determined that at the time of registration, the patient did not satisfy each and every eligibility criteria for study entry. The patient will go directly to off study.
 - If the patient had cfDNA testing, all data up until the point of confirmation of ineligibility must be submitted
- 13.2 A patient is deemed a *cancel* if he/she is removed from the study for any reason other than ineligibility before any study-specific activities take place. On-study material must be submitted. No further data submission is necessary.
 - If the patient never had cfDNA testing, only on-study material must be submitted

14.0 Body Fluid Biospecimens

14.1 Summary Table of Research Blood/Blood Products for This Protocol

Indicate if specimen is mandatory or optional	Collection tube description and/or additive (color of tube top)	Volume to collect per tube (number of tubes to be collected)	Blood product being processed and submitted by participating site	Baseline	Storage /shipping conditions ⁴
Mandatory	Streck tube	10 mL (2)	Whole blood	X	Room
					temperature

- NOTE: If the patient has received Guardant360 testing ≤60 days of registration, these test results will be accepted for study and cell-free DNA analysis will not be repeated; no blood drawn at baseline. To receive test results, see section 7.0.
- 14.2 Kits are required for this study.
 - 14.21 In order to receive an initial kit shipment and access to the Guardant portal, fill out the Guardant Site Setup form for each treating location and email it to ACCRU at
 - 14.22 ACCRU will notify Guardant Health once each site is activated and will help facilitate portal access requests and the initial kit shipment. Guardant Health will provide portal access and and will ship the initial supply of kits to each site. Following the initial shipment, each site can request that kits be refreshed/replaced by completing the "Kit Reorder Form" and emailing it to Guardant Health Client Services Team at
- 14.3 Shipping and Handling
 - 14.31 Guardant360 (Streck Tube)
 - 14.311 Complete the Test Requisition Form and barcode labels.
 - 14.312 Ship tubes the same day as collection with properly prepared gel packs. Do not freeze gel packs. Use as is.
 - 14.313 Place the kit into the preprinted FedEx Clinical Pak and call FedEx for a pickup to be shipped to Guardant Health.
 - 14.314 Detailed Blood Draw and Shipping Instructions are located on the ACCRU website under Manuals and Forms.
- 14.4 Return of Genetic Testing Research Results

Results of CLIA-certified assays (e.g., Guardant 360) are permitted to be shared with

patients and their treating physicians. The return of genetic testing research results do not apply to patients who completed Guardant360 testing outside of the COLOMATE trial.

